## 1. Protocol Synopsis

Title	
PREEMER TRIAL - Prophylactic mesh versus no mesh in midline emergency laparotomy closure for prevention of incisional hernia: a multicenter, double- blind, randomized controlled trial
 
Light weight synthetic mesh for incisional hernia prevention after emergency laparotomy

Principal Investigator	[name] M.D. Oulu University Hospital
Study Group	
[name] M.D. Ph.D. Oulu University Hospital
 
[name] M.D. Oulu University Hospital
 
[name] M.D., Ph.D. Helsinki University Hospital
 
[name] M.D., Ph.D. Helsinki University Hospital
 
[name] M.D., Ph.D. Helsinki University Hospital
 
[name] M.D., Ph.D. Helsinki University Hospital
 
[name] M.D., Ph.D. Hospital AZ Maria Middelares, Ghent, Belgium
 
[name] M.D., Ph.D. Oulu University Hospital

Study Population	
Patients, who have an emergency midline laparotomy for any gastrointestinal reason, will be randomized in a 1:1 ratio either to mesh group with a retrorectal prophylactic self-gripping mesh or to control group with 4:1 small stitch closure by continuous monofilament suture.

Study Objective	Compare light weight synthetic prophylactic mesh to no mesh in midline emergency surgery laparotomy closure for prevention of incisional hernia
Study Design	Randomized, double-blinded, multi-center study
Study Endpoints	
Primary Endpoint:
 
Incidence of incisional hernia, either symptomatic or asymptomatic detected clinically and/or radiologically within 2 years from surgery.
 
Secondary Endpoints:
 
 
• Comprehensive Complication Index within 30 days from surgery
 
• Surgical site infection (SSI) rate defined by CDC classification of surgical site infection within 30 days follow-up
 
• Fascial rupture within 30 days from surgery
 
• Incidence of Incisional hernia within 5 years follow-up
 

	
 
• Incisional hernia repair rate within 2 and 5 years after surgery
 
• Re-operations due to mesh- or hernia within 2 and 5 years from surgery
 
• Quality of life (RAND-36, AAS, PROMIS) within 30 days, 2 and 5 years from surgery
 
• Medico-economic explorative measures 
 
◦ Time to create the retrorectal space and insert the mesh
 
◦ Length of stay
 
◦ Costs of materials used to close the abdomen
 
◦ Length of sick leave
 
 
 

	
At least 244 subjects will be enrolled in this study (122 per group, including 20% off lost to follow-up during 2 years interval).
 
All patients undergoing midline emergency laparotomy during the enrollment period will be screened for inclusion and exclusion criteria and recorded at study sites in order to identify any selection bias.

Randomization	
Patients having emergency midline laparotomy for any gastrointestinal indication and fulfilling the inclusion criteria, will be randomized prior to surgery after giving informed consent to the study.
 
Patients are randomly allocated (1:1 ratio) either to an intervention group or a control group according to a computer-generated list compiled by a biostatistician otherwise uninvolved in the clinical care of trial patients.
 
Allocation will be stratified according to BMI (<30 and <math>\geq 30\text{kg/m}^2</math>), history of previous midline laparotomy and age (<65 and <math>\geq 65</math>- years) and blocked within strata using random permuted blocks (block size 2, 4, 6 and 8). A separate randomization list will be created for each participating center.

Total Study Duration	
Approximately 7-8 years:
 
 
• Site start-up: 3 months
 
• Study Enrollment: 24 months
 
• Short term follow-up: Discharge, 30 days
 
• Long term follow-up: 2 years and 5 years
 

Inclusion/ Exclusion Criteria	
Study Inclusion:
 
 
• Midline emergency laparotomy for any gastrointestinal indication
 
 
Study Exclusion:

Number of  
Patients

- Previous ventral hernia repair with mesh in the midline
  - Previous inguinal or femoral hernia repair by any technique with mesh is accepted
- Previous WHO class of physical activity 3-4 (WHO 3 more than 50% of time at rest, WHO 4 stays at rest most of the time)
- Relaparotomy
- Indication for laparotomy is incarcerated hernia
- Pregnant or suspected pregnancy
- <18 years
- Metastatic malignancy of any origin
- Planned ostomy
- Patients living geographically distant and/or unwilling to return for follow-ups
- No informed consent
- Subject participates in another RCT

Intra-operative exclusion criteria applicable for both randomization groups

- Abdomen is left open
- Second look laparotomy planned
- Inability to keep the mesh securely out of the peritoneal cavity or close the anterior fascia
- Intra-abdominal malignancy diagnosed at the operation
- >2 cm hernia in midline
- Ostomy made at the operation

Human Subjects Protection	
Full approval of Ethical Committee of Oulu University Hospital approved by Institutional revision board in each participating hospital, with all other specific approvals, must be obtained for the study prior to study initiation at the site. Subjects must sign an EC-approved Informed Consent Form (ICF) prior to enrollment into this study.
 
As the previous research on synthetic mesh utilized as prophylaxis at emergency laparotomies is scarce, an analysis of the complications and risks will be evaluated for safety reasons after 30 patients have been randomized to both groups and reached 30 days follow-up. For the same reason, there will be further analysis on the complications of the mesh

---------------------------	---

	after 30 patients randomized to each group have reached the 2 years follow-up.
Data Collected	
Data collected will include the following:
 
 
Demographics, Patient Characteristics, and Pre-operative History: Age, BMI, previous surgical history, comorbid conditions and medications, history of smoking, previous hernias and hernia related operations
 
Intra-Operative Assessment: Prophylactic antibiotics, ASA, presence of hernias in midline, rectus diastasis, operative time, blood loss, contamination class, surgical procedure, ostomy creation and its' location from midline, length of wound, length and type of suture materials used, drains, vacuum assisted closure, other temporary closure method used, skin closure.
 
Post-Operative Assessment through Discharge: Surgical site infections, complications, re-operations, pain score (VAS) at discharge, Quality of life questionnaire, seromas, burst abdomen, fascial dehiscence, length of stay, mesh removals, length of planned sick leave, place of discharge.
 
Follow-Up Assessments: complications, clinically and/or radiologically detected hernia rate, procedure- or incisional hernia-related readmissions, procedure- or incisional hernia-related reoperations, QoL (RAND-36, AAS, PROMIS) and economic measures, pain of abdominal wall, long-term seromas.
 
 
Data will be collected 2 and 5 years postoperatively.

Data collection	Primary data collection will be performed by participating surgeons using electronical database.
Statistical Analysis	All analyses will be performed by or under the guidance of professional statistician and following the CONSORT guidelines. The primary endpoint as well as other categorical data will analysed by $\chi^2$ -test or Fisher's exact test. Ninety-five % confidence intervals (95% CI) are presented for between group differences (effect sizes). The incidence of hernia will also be analyzed using Kaplan-Meier analysis. Student's t-test or

	
Welch test will be used for continuous variable, the latter if assumption of homogenous variances does not hold.
 
Linear mixed model (LMM) or generalized linear mixed model (GLMM) will be used for repeatedly measured data, the previous for continuous data and latter for categorical data.

Finance	
Materials and visits are funded by hospital districts as part of treatment expenses. External funding will be applied to cover the costs caused by imaging.

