### 4. Study Design

This study is a multicenter, double-blinded, randomized controlled trial. Parameters will be collected prospectively after randomization. All enrolled subjects will undergo assessments at the following intervals: pre-operative, operative, discharge, 30 days, 2- and 5-years post-surgery. A

description of the study visits and required study procedures is summarized in Section 12, Schedule of events.

All patients are evaluated both clinically and radiologically at 2 years after index procedure in

order to diagnose clinical and/or radiological incisional hernia. The follow up will continue until 5 years after the surgery to assess long-term results and safety.

Ultrasound with and without Valsalva maneuver will be performed to all patients 2 years after

surgery. The extent of the fascial defect and hernia sac volume (ie. the volume of incisional hernia) are measured and graded according to the European hernia society criteria. (46)

If there is a suspicion of symptomatic or asymptomatic incisional hernia according to clinical

assessment and ultrasound findings are inconclusive, CT scan is required to verify the diagnosis of IH. If a patient have had no imaging done for any reason, the result of clinical

evaluation is

recorded. In case of several imaging modalities accomplished, all results are recorded. All study

PREEMER TRIAL 12

patients are guided to contact their study site in case of any suspicion of incisional hernia at any point during follow up.

Quality of life will be measured using RAND-36, Activities Assessment Scale (AAS) and PROMIS questionnaire at all follow-up visits at 1 months, 2 years and 5 years as well as when a hernia is diagnosed.

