## 6. Study Endpoints

### 6.1 Primary Endpoints

The primary endpoint of this study is the incidence of incisional hernia, either symptomatic or asymptomatic detected clinically and/or radiologically within 2 years after surgery.

In case of inconsistency between clinical and radiological evaluation exists or either one is missing for any reason, a following definition of primary endpoint will be used:

Clinical exam result	Imaging result	Primary endpoint
Hernia	Hernia	Hernia

No hernia	Hernia	Hernia
Hernia	No hernia	No hernia
No hernia	No hernia	No hernia
Hernia	Missing	Hernia
No hernia	Missing	No hernia
Missing	Hernia	Hernia
Missing	No hernia	No hernia

If there is inconsistency between ultrasound and CT scan, the result of CT scan will be applied.

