### 10.3. Study Plan

[figure not shown]
*Figure 1 Flow Chart*

Intend to treat population  
reaching 30 days control

Intent to treat  
population  
reaching 2 years  
control

Intent to treat  
population  
reaching 5 years  
control

Data will be collected at baseline, operative procedure, discharge, 30 days, 2 years and 5 years. Specific databases (Hoitoilmoitusrekisteri HILMO, Tilastokeskus) may be used to collect data of patients' survival and operations done to patient outside study sites. If there is any suspicion of

PREEMER TRIAL 17

incisional hernia raised at any point of the follow-up, the patient is advised to contact the study site and additional clinical evaluation and ultrasonography if needed is arranged. The data will be collected using electronical CRFs and software designed for this study.

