### 19.3 Endpoint analysis

All analyses will be performed primarily according to modified intention to treat (ITT) principle.

Patients who fulfill exclusion criteria intraoperatively (after randomization) will not be included in the analyses. Per protocol analyses will be used as safeguard against the risk of falsely claiming

PREEMER TRIAL 30

equality/superiority. The primary endpoint will be the incidence difference of IHs with 95% confidence interval between the study groups during 2-years follow up. Secondary outcomes are

listed previously. The primary endpoint as well as other categorical data will be analyzed by the  $\chi^2$ - test or Fisher's exact test. Student's t-test or Welch test will be used for continuous variable, the

latter if assumption of homogenous variances does not hold. The incidence of hernia will also be

analyzed using Kaplan-Meier analysis.

The linear mixed model (LMM) or generalized linear mixed model (GLMM) will be used for repeatedly measured data, the previous for continuous data and latter for categorical data. Multiple imputations of missing outcome data will be used for sensitivity analyses.

Prospectively

planned subgroup analyses are as follows: BMI>30, previous hernia and contamination class 4.

However, sample size calculation is done only for the primary end point and subgroup analyses are hypothesis generating only. The statistical programs SPSS (IBM Corp.

Released 2016. IBM SPSS

Statistics for Windows, Version 24.0. Armonk, NY: IBM Corp) and SAS (version 9.4, SAS Institute Inc., Cary, NC, USA) will be used for the analyses.

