## 20.1. Publication Plan

The protocol of the trial will be published at the beginning of the trial. The results concerning the primary end point and results of secondary endpoints within 2 years follow up will be published once included patients have reached 2 years follow-up. The results of 5 years follow up will be published.

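### Must the protocol say how events are dated in its additional Kaplan-Meier analysis, when the only scan given to everyone falls at 2 years ±30 days?

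*Protocol*

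**What the plan says.** The primary endpoint (Section 6.1) is hernia yes or no by 2 years, "either symptomatic or asymptomatic detected clinically and/or radiologically". Section 19.3 makes the between-group incidence difference with its 95% confidence interval the primary result, tested by chi-square or Fisher's exact test. Kaplan-Meier is an addition in two places: the synopsis ("The incidence of hernia will also be analyzed using Kaplan-Meier analysis") and Section 19.3, where incidence is also to be "analyzed using Kaplan-Meier analysis". Neither gives a rule for dating events or censoring hernia-free patients.

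Section 4 fixes the one systematic scan: "Ultrasound with and without Valsalva maneuver will be performed to all patients 2 years after" surgery. Section 12 allows ±30 days around it. Between visits, detection depends on suspicion: "patients are guided to contact their study site in case of any suspicion of incisional hernia at any point during follow up" (Section 4), after which "additional clinical evaluation and ultrasonography if needed is arranged" (Section 10.3, Study Plan). The 5-year ultrasound is also done only on suspicion. Under Section 20.1 the 2-year results "will be published once included patients have reached 2 years follow-up".

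**The concern.** Kaplan-Meier takes each event time as exactly observed. Here, a hernia without symptoms is found only when the patient attends the 2-year scan. It arose at some unknown time since the last hernia-free assessment, and its recorded date is the appointment.

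If actual dates are used, most events and most hernia-free censorings fall inside a 60-day window centred on the time at which the curve would be read. The 2-year value then reflects appointment timing as well as incidence. The 2-year results are published on their own, so a curve beside the primary table could appear to contradict it for scheduling reasons alone. An unstated rule could also be chosen after the data are seen.

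**Working it through.** **Inputs.** Control 25%, mesh 10% and 97 per group (Section 19.1); scan window of days 730−30 to 730+30, that is 700 to 760 (Section 12). The protocol gives neither the spread of visits within the window nor the share of hernias found earlier. Both are assumptions and are varied below.

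**1. The plan's own figure.** Unpooled two-proportion formula, two-sided 5%, 80% power: (1.96 + 0.8416)² × (0.25×0.75 + 0.10×0.90) / 0.15² = 96.8, so 97. With 20% dropout: 97/0.80 = 121.25, so 122. Both stated sizes are reproduced, and neither uses event dates.

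**2. Nominal dating.** Put all 2-year-visit findings, positive and negative, at one common time, and use real dates only for earlier diagnoses. With n patients, a early hernias, b hernias at the visit and no dropout, S(2 years) = (n−a)/n × (n−a−b)/(n−a) = (n−a−b)/n. This is exactly the complement of the observed proportion. Simulation gives 25.0 to 25.1% and 10.0 to 10.2%, including with 20% dropout.

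**3. Actual dates, read at day 730.** Take visits uniform over the 61 days and all hernias found at the scan. The share of visits made by day 730 is 31/61 = 0.508.
- Hernia-free patients kept at risk: 0.25×0.508 = 12.7% and 0.10×0.508 = 5.1%, a difference of 7.6 points instead of 15.
- Hernia-free patients censored at their own visit: each visit is an event with probability p and otherwise a censoring, so S = (1−u)^p at visit share u. This gives 1−0.492^0.25 = 16.3% and 1−0.492^0.10 = 6.9%, a difference of 9.4 points.
- Half the hernias found early, kept at risk: 0.25×(0.5 + 0.5×0.508) = 18.9%.

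Simulation agrees (12.5 to 12.8%, 16.2 to 16.3% and 18.9% in controls).

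**4. Other visit patterns.** Simulated control estimate at day 730, 97 per arm, as the share found early rises from 0 to 70%:

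| Visit days | Kept at risk | Censored at own visit |
|---|---|---|
| Uniform 700–760 | 12.8 to 21.3% | 16.3 to 22.6% |
| Centred on 730, SD 10 | 13.0 to 21.5% | 16.5 to 22.8% |
| Centred on 740, SD 10 | 4.3 to 18.8% | 4.6 to 18.9% |
| Centred on 720, SD 10 | 21.3 to 23.9% | 37.0 down to 30.2% |
| Nominal 2 years | 25% | 25% |

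In the first two patterns, the Kaplan-Meier difference at day 730 departs from the observed difference by 2 points or more in 49 to 94% of simulated trials.

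**5. Actual dates, read at day 760.** If hernia-free patients stay at risk, the curve is right: 25% and 10%. If they are censored at their own visit, the risk set empties while events still occur. With all hernias found at the scan and no tied dates, 1−∏(1−p/k) over k = 1 to 97 gives 74.0% and 40.8%. With integer dates, uniform visits and 0 to 70% found early, the control value is 69.5% down to 45.0%, with a median of only 4 to 9 control patients at risk at the last event.

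**6. Comparison between arms.** The protocol names no log-rank test. If one were run (25% found early, censored at the visit), its size is 5.4% on actual dates against 4.9% on nominal dates, and its power 75% against 78%.

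**What drives the effect.** The data are just as interval-censored under nominal dating, yet the 2-year level is then exact. The direct cause is the scatter of event and censoring dates within the window. Interval censoring itself affects the shape of the curve before 2 years, which shows when hernias were detected and not when they arose.

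**The case for a change.** The strongest case for a change is that the method and the visit schedule are both fixed in the protocol, and together they give a correct 2-year reading only under some dating and censoring choices. Leaving the choice open lets the control estimate run from under 20% to over 50%, and one sentence would close it.

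The arithmetic behind this stands. It does not show an error in the document, for three reasons. First, the problem arises only if analysts use raw appointment dates and then either read the curve at exactly day 730 or let it run out as patients are censored. No section asks for any of these. Second, the protocol frames its results by nominal milestone (Sections 6.1, 19.3 and 20.1, and the populations in the flow chart), which points towards nominal timing. Third, event dating for a supporting curve is normally settled in the statistical analysis plan, which may exist but is not at hand, and the protocol requires a professional statistician's involvement.

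One defence should not be overstated. Keeping hernia-free patients at risk makes the actual-date curve correct at the end of the window, but at the time of the 2-year report the last patients enrolled may have little follow-up beyond their scan.

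**Conclusion.** No change to the protocol is called for. The effect is real but conditional: at the planning rates, actual-date curves read at day 730 could show anything from about 4% to 37% in controls instead of 25%, in a direction set by assumed visit timing and censoring. It disappears under the ordinary convention of placing 2-year findings at 2 years. The text as written is fully compatible with that convention or with an interval-censored estimate.

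The consequences are also limited. The curve is a supplement. The primary test, the incidence difference and the sample size are untouched, and a between-arm comparison keeps close to its nominal error rate when visit timing is alike in both arms. This is a gap that a competent analyst fills as a matter of routine in the analysis plan. The conclusion rests on the protocol nowhere prescribing actual dates or a day-730 reading; an analysis plan that did prescribe them would need a second look.

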## 2.

### Introduction

#### 2.1 Incisional hernia incidence

Incisional hernia (IH) is a common complication of abdominal wall surgery. Its' incidence varies greatly (2–30 %) among studies (1-3) . The incisional hernia incidence is influenced by several factors, such as closing technique (4,5) , follow-up time (6) and the modality of radiological investigations,(7,8) , patient characteristics and comorbidities as well as indication and type for surgery(9).

#### 2.2. Incisional hernia etiology

The etiology of incisional hernia is multimodal. The site and orientation of the incision has an influence on the IH rates. Non-midline incisions—both paramedian and transverse—carry a significantly reduced risk of IHs compared to midline incisions (10-11) . Suturing technique and the suture material used affect the hernia rate as well. Taking small bites of 5 mm with an intersuturing space of 5 mm with slowly absorbable monofilament suture results in a lower hernia incidence compared to large bite mass suturing (4-5, 12-14) .

There is lack of evidence of basic biological pathogenesis of incisional hernias (IH). Specific features of connective tissue and the quality of fibroblasts are proposed to have an influence on the risk for hernia formation (15). The inflammatory response after an incision results in the fibroproliferative phase. Incisional hernia may be a result of disturbance in the fibroblast proliferation in the laparotomy wound matrix (16).

Fascial ischemia is presumed to be one crucial factor in the development of an IH. The fascia is hypovascular and a wound experiences hypoxic stress immediately after surgical incision, which has been considered a major risk factor for wound failure. Hypoxia interferes with angiogenesis and the healing process (17). The revascularization at the wound site is critical to improve healing response (18). Good surgical skills and maintaining sufficient perfusion in the wound area are important issues to be noted (19).

Along with previously mentioned physiological alterations, patients' comorbidities and characteristics can predispose them to develop of a hernia (9) . Connective tissue disorders increase the risk for herniation among various other patient-related factors (20, 21). One of the most common risk factor, that increase the likelihood of development an IH is smoking (75 %) (22). As a result of an analysis of 14,618 patients, Bosanquet in his review and meta-regression determined the factors affecting midline IH rates: diabetes mellitus, obesity, cachexia, increasing age, male sex, chronic obstructive pulmonary disease (COPD), a history of or operation for an abdominal aortic aneurysm (AAA), anaemia, smoking, corticosteroids and surgical site infection (SSI). Summarising the results of 56 publications, the prevalence of IHs after midline laparotomy was 12.8 % (range: 0 to 35.6 %) with a mean follow-up time 23.7 months (21) .

### 2.3 Incisional hernia definition and evaluation

Most commonly, an IH is a bulge or a gap in the area of a postoperative scar. It can be asymptomatic but is often associated with symptoms, such as pain, cosmetic discomfort, bowel obstruction or even incarceration (23,24) . Valsalva's manoeuvre is used to make the hernia more apparent clinically: the increase in intra-abdominal pressure causes the hernia sac to enlarge and protrude through the anatomic defect. The clinical examination is recommended to be performed in both standing and supine positions.

The examination can be difficult in obese patients or in postoperative situations in which incisional hernia may be difficult to distinguish from a postoperative complication, such as a hematoma, abscess or seroma. The radiological imaging (ultrasound

(US), computed tomography (CT) or magnetic resonance (MRI)) is useful in specifying the diagnosis (8,25-27) .

A standardised dynamic abdominal sonography for hernias offers a safe and a low-cost diagnostic tool with great specificity and positive predictive value (28) . A CT scan can also be an option in some cases like when planning operative treatment, although it induces a radiation load for patients.

When evaluating the IH rate, the difference between physical examination and imaging modalities (ultrasound or computer tomography) is important in terms of accuracy (29,30) . A standardised examination and dynamic evaluation by ultrasound of the abdominal wall is recommended in evaluating a possible hernia (14,31). Incidence of IHs increases during a follow-up study time from 12.6 % at 12 months to 22.4 % at 36 months(6,32,33).

There is a great diversity of abdominal wall IHs. During the early years of 2000 the first proposals for the classification of incisional ventral hernias were published. Through 2009, there were several proposals for classifying IHs according to defect size, recurrence and topography to some extent, but none of these achieved wide recognition or routine use(34-36). In 2009, the European Hernia Society (EHS) published a formula to classify primary and incisional abdominal wall hernias (36).

